### **9.5.2. Palatability of SOF oral granules**

Palatability of SOF oral granules will be summarized using descriptive statistics by appropriate age group, by genotype, by overall and by age group and genotype.

### **9.5.3. Adverse Events**

Clinical and laboratory AEs will be coded using the Medical Dictionary for Regulatory Activities (MedDRA). System Organ Class (SOC), High-Level Group Term (HLGT), High-Level Term (HLT), Preferred Term (PT), and Lower-Level Term (LLT) will be attached to the clinical database.

Events will be summarized on the basis of the date of onset for the event. A treatment-emergent adverse event will be defined as any new or worsening adverse event that begins on or after the date of first dose of study drug up to the date of last dose of study drug plus 30 days.

Summaries (number and percentage of subjects) of treatment-emergent adverse events (by SOC and preferred term) will be provided by cohort:

- All AEs,
- All study drug-related AEs,
- Combined Grade 2, 3 and 4 AEs,
- Combined Grade 3 and 4 AEs,
- Combined Grade 2, 3 and 4 study drug-related AEs,
- Combined Grade 3 and 4 study drug-related AEs,
- All AEs that caused permanent discontinuation from study drug,
- All AEs that caused change in dose or temporary interruption of study drug,
- All SAEs (including death), and
- All study drug-related SAEs

All AEs collected during the course of the study will be presented in data listings.

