### **8.3. Investigator Requirements and Instructions for Reporting Adverse Events and Serious Adverse Events**

Requirements for collection prior to study drug initiation:

After informed consent, but prior to initiation of study medication, the following types of events should be reported on the case report form (CRF/eCRF): all SAEs and adverse events related to protocol-mandated procedures.

All SAEs, regardless of causal relationship, that occur after the subject first consents to participate in the study (i.e., signing the informed consent) and throughout the duration of the study, including the protocol-required 24-week post treatment follow-up period, must be reported to the CRF/eCRF database and Gilead Drug Safety and Public Health (DSPH) as instructed. This also includes any SAEs resulting from protocol-mandated procedures performed from screening onwards.

All AEs, regardless of causal relationship, that occur from initiation of study medication until 4 weeks after last administration of study IMP must be reported to the CRF/eCRF database as instructed.

All AEs should be followed up until resolution or until the adverse event is stable, if possible. Gilead Sciences may request that certain AEs be followed beyond the post-treatment follow up period.

Investigators are not obligated to actively seek SAEs after the 24 week post-treatment follow-up period. However, if the investigator learns of any SAEs that occur after this time and/or if patient is enrolled into the long term follow-up registry, GS-US-334-1113 study, and/or eCRF database has been locked and the event is deemed relevant to the use of IMP, he/she should promptly document and report the event directly to Gilead DSPH within 24 hours of awareness. Gilead DSPH contact information is as follows: Email: [Safety\\[contact]](mailto:[contact]) or [contact]. All AEs and SAEs will be recorded in the CRF/eCRF database within the timelines outlined in the CRF/eCRF completion guideline.

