**Appendix Table 3. Treatment Phase: Post Treatment Visits Following Primary Study**

	4 Weeks Post Treatment	12 Weeks Post Treatment	24 Weeks Post Treatment
Clinical Assessments			
Vital Signs, Body weight and Height	X	X	X
Symptom-directed Physical Exam	X	X	X
AEs	X	X d	X d
Concomitant Medications	X		
Quality of Life Survey a		X	X
Tanner Pubertal Stage Assessment		X	X
Bone Age Assessment			X
Pregnancy Prevention Counseling c	X	X	
Laboratory Assessments			
Hematology, Chemistry	X	X	
HCV RNA	X	X	X
Viral Sequencing b	X	X	X
Urine Pregnancy Test e	X	X	X

a Quality of life survey will be completed by all subjects at 12-Week and 24-Week Post Treatment visits if a site is approved to use the survey. Subject is to review questionnaire with a parent/guardian and write/mark answers directly onto the questionnaire.

b Plasma samples will be collected and stored for potential HCV sequencing and other virology studies

c Female subjects of childbearing potential should be provided with Urine Pregnancy Test Kits, instructed on their use and requested to continue to self-monitor for pregnancy for 6 months after their last dose of RBV. If required by regulations, additional pregnancy tests beyond 6 months may be added. The subject should be contacted every 4 weeks and asked to report results of the urine pregnancy tests. If a positive urine pregnancy test is reported, the subject should return to the clinic for a serum pregnancy test.

d At Post Treatment Week 12 and 24, only SAEs will be captured

e Including partner pregnancy prevention for male participants (subjects 12 to < 18 years of age and subjects < 12 years of age at the discretion of the Investigator based on subject's pubertal status).

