7.1.5. Treatment-Emergent Adverse Events

7.1.5.1. Definition of Treatment Emergent

Treatment-emergent adverse events (TEAEs) are defined as one or both of the following:

- Any AEs with an onset date on or after the study drug start date and no later than 30 days after permanent discontinuation of study drug.
- Any AEs leading to premature discontinuation of study drug.

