7.1.6. Summaries of Adverse Events and Deaths

A brief high-level summary of TEAEs will be provided by treatment group and by the number and percentage of subjects who had the following: any AE; any AE of Grade 3 or above; any AE of Grade 2 or above; any treatment-related AE; any treatment-related AE of Grade 3 or above; any treatment-related AE of Grade 2 or above; any SAE; any treatment-related SAE; any AE that led to premature discontinuation of any study drug; any AE that led to premature discontinuation of SOF; any AE that led to premature discontinuation of RBV; any AE that led to modification or interruption of any study drug; any AE that led to interruption of SOF; any AE that led to modification or interruption of RBV. All deaths (including those that are treatment emergent and those that are not treatment emergent) observed during the study will also be summarized and included in this table. Additional brief high-level summary of TEAEs will be provided by treatment group defined in [Table 3-2](#) for 3 to < 6 years of age subjects.

Adverse event summaries will provide the number and percentage of subjects with TEAEs by SOC and PT, by treatment group based on the Safety Analysis Set as follows:

- All AEs
- AEs of Grade 3 or above
- AEs of Grade 2 or above
- All treatment-related AEs
- Treatment-related AEs of Grade 3 or above
- Treatment-related AEs of Grade 2 or above
- All SAEs
- All treatment-related SAEs

- All AEs leading to premature discontinuation of study drug
- AEs leading to premature discontinuation of SOF
- AEs leading to premature discontinuation of RBV
- AEs leading to modification or interruption of any study drug
- AEs leading to interruption of SOF
- AEs leading to modification or interruption of RBV

Multiple events will be counted only once per subject in each summary. Adverse events will be summarized and listed first in alphabetic order of SOC and then by PT in order of descending incidence of the pooled treatment groups within each SOC. In summaries by severity grade, the most severe grade will be used for those AEs that occurred more than once in an individual subject during the study.

In addition to the above summary tables, TEAEs will be summarized by PT only, in order of descending incidence within the pooled treatment groups for:

- AEs that occurred in at least 5% of subjects within any treatment group
- AEs of Grade 3 or above
- All treatment-related AEs
- All SAEs

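### SAEs are collected to 24 weeks after treatment, but every planned SAE count stops at onset 30 days after the last dose, and later SAEs appear only in listings

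*Protocol*

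**What the plan says.** **Collection.** Protocol 8.3 requires SAEs, whatever their cause, to be reported from consent onward. The requirement extends "throughout the duration of the study, including the protocol-required 24-week post treatment follow-up period, must be reported to the CRF/eCRF database". The footnote to Appendix Table 3 confirms what the late visits are for: "At Post Treatment Week 12 and 24, only SAEs will be captured". All other AEs have a shorter period: Protocol 8.3 asks for those "that occur from initiation of study medication until 4 weeks after last administration of study IMP must be reported".

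**Tabulation in the protocol.** Section 9.5.3 defines a treatment-emergent event as a new or worsening one with this timing: "begins on or after the date of first dose of study drug up to the date of last dose of study drug plus 30 days". It then states: "Summaries (number and percentage of subjects) of treatment-emergent adverse events (by SOC and preferred term) will be provided by cohort". The list under that sentence includes a row for all SAEs, with deaths inside it, and a row for drug-related SAEs.

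**Tabulation in the SAP.** Section 7.1.5.1 sets the onset limit at "no later than 30 days after permanent discontinuation of study drug". It also counts any AE leading to premature discontinuation as treatment-emergent, with no onset limit. The SAE rows of the overview table and the tables by system organ class and preferred term in 7.1.6 are all summaries of treatment-emergent events. The overview table treats deaths differently: "All deaths (including those that are treatment emergent and those that are not treatment emergent) observed during the study will also be summarized".

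**Listings.** Protocol 9.5.3 lists every AE collected. SAP 7.1.6 plans an all-AE listing with a treatment-emergent flag, plus separate listings of SAEs and deaths.

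**Deviations.** SAP 7.11 reports no departure from the safety analyses in the protocol.

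**The concern.** Safety and tolerability is the primary objective of the Treatment Phase (Protocol 2). Two post-treatment visits collect SAEs and no other adverse events, yet neither document plans to count SAEs with onset in most of that period. A reader who takes the all-SAEs row as the study's SAE total could see 0% although SAEs were reported as the protocol requires.

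The late period is not empty of drug risk by the protocol's own account. Section 1.3 and Appendix 5 say that ribavirin accumulates in cells and is cleared slowly, and Appendix 5 extends contraception to 6 months after the last dose for females and 7 months for males. Section 8.5.2.1 makes any spontaneous abortion an SAE. Such an event in the third month after treatment, even if judged related to study drug, would enter no SAE number or percentage.

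Within the SAP overview table, deaths and SAEs also run over different windows, although Protocol 8.1.2 makes death a criterion for an SAE.

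**Working it through.** **Inputs.** Treatment lasts 12 weeks (84 days) for genotype 2 and 24 weeks (168 days) for genotype 3, and post-treatment follow-up lasts 24 weeks (168 days). Screening takes 28 days (all Protocol 3.2.2). The tabulation limit is 30 days after the last dose (Protocol 9.5.3, SAP 7.1.5.1). The Week 24 post-treatment visit has a window of ±5 days (Protocol 6.5.3).

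**The plan's own figure.** Protocol 3.2.2 gives a total of about 40 or 52 weeks. 4 + 12 + 24 = 40 and 4 + 24 + 24 = 52, so the inputs reproduce it. The documents give no figure for SAE time outside the tables.

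**Share of SAE collection time that feeds no SAE count, from first dose.** The formula is (168 − 30) / (treatment days + 168).

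| | Collected (days) | Tabulated (days) | Not tabulated (days) | Share |
|---|---|---|---|---|
| Genotype 2 | 84 + 168 = 252 | 84 + 30 = 114 | 138 | 138/252 = 54.8% |
| Genotype 3 | 168 + 168 = 336 | 168 + 30 = 198 | 138 | 138/336 = 41.1% |

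Of the post-treatment period alone, 138/168 = 82.1% lies outside the tables.

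**Sensitivity.**
- Moving the last visit by ±5 days gives 133/247 = 53.8% to 143/257 = 55.6% for genotype 2, and 133/331 = 40.2% to 143/341 = 41.9% for genotype 3.
- Measured from consent with a full 28-day screening, the days after day 30 are 138/280 = 49.3% and 138/364 = 37.9%.
- Adding the 28 pre-dose days, which the tables also leave out, gives 166/280 = 59.3% and 166/364 = 45.6%.

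**Exceptions to the 30-day limit.** The discontinuation criterion in SAP 7.1.5.1 has no onset limit, but an event that begins after treatment has ended can hardly be the reason treatment stopped. SAP 7.1.5.2 may bring in an occasional event with a missing or partial onset date. Neither changes the picture.

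**Deaths against SAEs.** Protocol 9.5.3 and SAP 7.1.5.1 both classify events by onset date.
- Fatal event with onset by day 30 and death in post-treatment Week 10: counted in the SAE row and in the deaths row.
- Fatal event with onset after day 30: counted in the SAP deaths row only.

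The protocol keeps deaths inside its treatment-emergent SAE row. The whole-study deaths count exists only in SAP 7.1.6.

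**The case against.** The strongest case for leaving the plan alone has five parts.

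1. The 30-day window is deliberate and consistent across both documents (Protocol 9.2.1.2, 9.5 and 9.5.4; SAP 7.2.2.1). Nothing promises a table of later SAEs. This stands, and the window itself is not at fault.
2. The tables are introduced as treatment-emergent summaries, and the deaths line states that it goes beyond them. A reader might infer that the SAP table contradicts itself, or that any late death would lack a matching SAE. The documents support neither reading. Two rows with openly different windows do not contradict each other, and the mismatch needs a fatal event that began after day 30.
3. Late SAEs are not lost. They are listed with a flag, and SAP 7.1.4 reconciles the SAE data with the sponsor's pharmacovigilance database. In a single-arm study of about 100 subjects, a listing can be read line by line. This also stands: the gap is in tabulation, not in data capture. But a listing gives no count, percentage or summary by system organ class.
4. An all-study SAE row beside the any-AE row would mix collection periods, and late SAEs are harder to attribute. Subjects without SVR are encouraged to discuss standard-of-care therapy (Protocol 3.1.2), and concomitant medication is recorded only to the 4-week visit (Protocol 5.6). This is a sound argument for a separate, labelled count, not for having none.
5. The primary safety endpoint is an AE leading to permanent discontinuation (Protocol 9.1.2), which this gap does not touch. That is correct and limits the importance of the point.

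**Conclusion.** The point holds as a gap in tabulation that is worth closing because closing it is cheap. Every planned SAE count is restricted to treatment-emergent events, so 138 days of required SAE collection per subject feed no SAE count. That is 55% of the time from first dose for genotype 2 and 41% for genotype 3. The figures assume full-length treatment, follow-up to the nominal Week 24 visit and the clock starting at first dose.

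A reader might infer that 41% to 55% of SAEs would go uncounted. That would follow only if SAEs occurred at a constant rate on and off treatment. The documents state no such rate, and the number affected could be zero.

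A second, smaller point is that the SAP counts deaths over the whole study whereas Protocol 9.5.3 keeps them inside the treatment-emergent SAE row. SAP 7.11 should say so.

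**What to change.** In SAP 7.1.6, keep the 30-day treatment-emergent rows as they are. Add a separately labelled count (n, %) of subjects with any SAE, and with any study-drug-related SAE, with onset after day 30 through post-treatment Week 24. Counting from first dose through end of study would also serve. Add a breakdown by system organ class and preferred term if any such events occur.

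Place the count apart from the any-AE rows, because non-serious AEs are collected only to 4 weeks after the last dose. Flag events that began after the start of other HCV therapy, where this is known. In SAP 7.11, record that the deaths window differs from Protocol 9.5.3.

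The cost is a few lines of SAP text and one small table from data already collected. The reported SAE percentage may rise slightly if the wider window is used, and late events will be harder to attribute to study drug. If the SAP is already final, SAP 1 provides for documenting the change in the clinical study report.

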### **9.5.4. Laboratory Evaluations**

Selected laboratory data will be summarized using only observed data. Absolute values and changes from baseline at all scheduled visits will be summarized. Graded laboratory abnormalities will be defined using the grading scheme in Grading of Laboratory Abnormalities provided in [Appendix 3](#).

Incidence of treatment-emergent laboratory abnormalities, defined as values that increase by at least one toxicity grade from baseline at any time post baseline up to and including the date of last dose of study drug plus 30 days, will be summarized by age group and overall. If baseline

data are missing, then any graded abnormality (i.e., at least a Grade 1) will be considered treatment emergent.

All laboratory abnormalities will be included in the listings of laboratory data.

### **9.5.5. Other Safety Evaluations**

#### **9.5.5.1. Tanner Pubertal Stage Assessment**

Tanner Stages ([Appendix 4](#)) will be summarized by baseline Tanner Stage using frequency and percentage.

### **9.6. Efficacy Analysis**

Efficacy will be evaluated using scheduled assessments of HCV RNA performed using COBAS® TaqMan® HCV Test, v2.0 for use with the High Pure System.

Efficacy analysis will be performed by age group, by GT, by overall, and by age group and GT for Treatment Phase.

All continuous endpoints will be summarized using an 8-number summary (n, mean, standard deviation, median, Q1, Q3, minimum, maximum). All categorical endpoints will be summarized by number and percentage of subjects who meet the endpoint definition.

#### **9.6.1. Primary Efficacy Analysis**

The key efficacy endpoint is SVR12 (HCV RNA < LLOQ 12 weeks after completion of treatment) in the FAS population. Point estimate and its 95% confidence interval will be provided.

#### **9.6.2. Secondary Efficacy Analysis**

The key efficacy endpoint of SVR12 will be compared with historical SVR12 rate of 80% from pegylated interferon + ribavirin for pediatric GT2 and 3 subjects {20280}, using two-sided exact one-sample binomial test at the 0.05 significance level.

The proportion of subjects with HCV RNA below LLOQ over time (including SVR endpoints SVR4 and SVR24) will be presented in Treatment Phase in tabular and graphical form.

Descriptive summaries and listings will be provided for additional efficacy evaluations including serum HCV RNA actual values and change from baseline, proportion of subjects with virologic failures, and other endpoints of interest including ALT normalization.

PPD

PPD

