The goal of HCV treatment in both pediatric and adult populations is eradication of the virus, thereby preventing hepatic inflammation, hepatic fibrosis, cirrhosis, and liver failure resulting in either death or need for liver transplantation. This goal, however, is limited by the nature of the disease and the fact that not all patients are suitable candidates for currently approved treatments. In addition, pediatric treatment is controversial as the current treatment options are limited and severe side effects and tolerability can significantly limit or preclude their use. Despite well-established guidelines for the treatment of HCV in adults, there is no universal consensus on when or if to treat chronic HCV infection in children. In 2010, the European Society for Paediatric Gastroenterology, Hepatology, and Nutrition (ESPGHAN) issued guidance for clinical trial development for chronic HCV infection in children {20286}. In the guideline, the ESPGHAN suggested that the primary goal of treatment in children is to eradicate the infection to prevent late complications. Hence, the goal is not the treatment of an ongoing liver disease, but rather the prevention of a future one.

PEG and weight-based RBV are currently considered the standard of care for the treatment of HCV infection in children. Current recommendations are that patients with GT-2 or GT-3 be treated with PEG+RBV for 24 weeks and those with GT-1 or GT-4 should receive 48 weeks of therapy. Successful treatment of GT-1, however, has proved very difficult to achieve in spite of additional therapy or increased duration of treatment. A number of pediatric studies have reported that despite 48 weeks of treatment, sustained virologic response (SVR24) was observed in only 36% to 53% of subjects with GT-1, while response rates were > 80% in subjects with GT-2 or GT-3 {20285}.

Most children treated with PEG+RBV experience at least 1 adverse event due to treatment {20285}. Although most of these events are mild to moderate in severity, many of them result in dose reductions of 1 or both of the drugs. The most common adverse events have consisted of influenza-like illness (91%), headache (62%), and injection site reactions (45%), often leading to poor compliance and/or discontinuation from treatment.

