### **9.9. Sample Size**

With approximately 50 subjects enrolled into each age group of Treatment Phase, a two-sided 95.0% confidence interval of the SVR12 rate will extend at most 11.1% in both directions from the observed SVR12 rate, assuming the expected SVR12 rate is 80%. In addition, a sample size of 100 subjects will provide over 80% power to detect an 11% improvement in SVR12 rate from 80% to 91% using two-sided one-sample binomial test at significance level of 0.05.

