6.1.2. Statistical Hypothesis for the Key Efficacy Endpoint

The null (H₀) and alternative (H₁) hypotheses used to assess the superiority of SOF + RBV relative to the historical SVR12 rate of 80% are as follows:

H₀: SVR12 rate = 80%

H₁: SVR12 rate ≠ 80%

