6.1.3. Analysis Methods for the Key Efficacy Endpoint

A sequential test method was used to firstly perform the above statistical test in the adolescent subjects (ie, 12 to < 18 years of age). The SVR12 rate for adolescents was compared with the historical SVR12 rate of 80% using a 2-sided exact 1-sample binomial test at the 0.05 significance level. The test in adolescents was described in a separate SAP for Adolescents SVR12 Analysis. Only if the superiority is demonstrated in adolescents, the SVR12 rate in the remaining subjects (ie, children aged 3 to < 12 years) will be compared with 80% at the 0.05 significance level.

The point estimates of SVR12 rate and 2-sided 95% exact CI based on Clopper-Pearson method will be provided for the SVR12 rate by treatment group and total in each age group {Clopper 1934}.

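### Rejecting a fixed 80% SVR12 rate does not by itself show an advantage over paediatric PEG+RBV, which the protocol's own background puts above 80%

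*Protocol*

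**What the plan says.** Protocol 9.6.2 sets the comparison: SVR12 "will be compared with historical SVR12 rate of 80% from pegylated interferon + ribavirin for pediatric GT2 and 3 subjects". It cites one source for the 80%. The method is given as "using two-sided exact one-sample binomial test at the 0.05 significance level".

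SAP 6.1.2 states hypotheses of SVR12 equal to 80% against not equal to 80%, "used to assess the superiority of SOF + RBV relative to the historical SVR12 rate of 80" per cent. SAP 6.1.3 tests adolescents first and makes the children's test depend on that result: "Only if the superiority is demonstrated in adolescents, the SVR12 rate in the remaining subjects" aged 3 to under 12 are to be compared with 80%. SAP 6.4 confirms that these age-group tests replace the protocol's single test in all treated subjects. SAP 6.1.3 also plans exact two-sided 95% Clopper-Pearson intervals by treatment group and for each age group in total.

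Protocol 1.1 describes earlier paediatric PEG+RBV studies from a different source. On genotype 1 it says "sustained virologic response (SVR24) was observed in only 36% to 53% of subjects with GT-1". On the two genotypes enrolled in this trial, the same sentence adds "while response rates were > 80% in subjects with GT-2 or GT-3". It gives no upper figure, sample size or interval.

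Neither document shows how 80% was derived, reconciles it with the background statement, or examines the conclusion at another benchmark.

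**The concern.** The label in Protocol 9.6.2 makes 80% stand for PEG+RBV. Protocol 1.4 and 1.6 present SOF+RBV as an expected improvement on that standard of care, including in efficacy. A reader of the report will naturally take superiority over the historical rate to mean better than PEG+RBV.

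That step holds only if the PEG+RBV rate is no more than 80%, and the protocol's own background puts it above 80%. The binomial test treats 80% as a known constant, so its error rate protects against SVR12 being 80%. It does not protect against SOF+RBV being no better than PEG+RBV. At stake is the wording of the only hypothesis test planned for SVR12, and the adolescent result also decides whether children are tested at all.

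**Working it through.** **Inputs**
- Null rate 80%, exact two-sided test at 0.05: Protocol 9.6.2 and SAP 6.1.2.
- Group size about 50, taken as exactly 50: Protocol 9.9 and SAP 1.3.
- Groups tested: adolescents, then children aged 3 to under 12: SAP 6.1.3.
- True PEG+RBV rate: only above 80% (Protocol 1.1). The values 81%, 82% and 85% below are assumptions.

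**1. The plan's own power figure.** Protocol 9.9 says "a sample size of 100 subjects will provide over 80% power to detect an 11% improvement in SVR12 rate from 80% to 91" per cent. For N = 100 the smallest r with P(X ≥ r | 0.80) ≤ 0.025 is 89, with tail probability 0.0126. Power is P(X ≥ 89 | 0.91) = 0.812. Under the minimum-likelihood version of the exact test r is 88 and power is 0.886. Both exceed 80%, so the arithmetic is right on its own inputs. It belongs to the pooled test that SAP 6.4 replaced.

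**2. Rejection rule at n = 50.**
- P(X ≥ 45 | 0.80) = 0.048, above 0.025.
- P(X ≥ 46 | 0.80) = 0.0185, below 0.025.

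Superiority is therefore declared at 46/50 or more. The minimum-likelihood version gives the same boundary (two-sided p = 0.079 at 45/50 and 0.033 at 46/50).

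**3. Chance of declaring superiority when SOF+RBV equals PEG+RBV at rate p.** This is P(X ≥ 46 | n = 50, p) = Σ C(50, x) pˣ (1 − p)⁵⁰⁻ˣ over x = 46 to 50, for one age-group test taken alone:

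| Common rate p | Probability |
|---|---|
| 80% | 1.8% |
| 81% (assumed) | 2.7% |
| 82% (assumed) | 4.0% |
| 85% (assumed) | 11.2% |

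The probability passes 2.5% once p exceeds about 80.8%. For both steps to succeed in independent groups with the same rate, the figure is squared: at 85%, 0.112 × 0.112 = 1.3%.

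**4. What the planned interval excludes.** The lower limit L solves P(X ≥ x | n = 50, L) = 0.025; for 50/50, L = 0.025^(1/50) = 0.929.

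| Responders | Lower 95% limit |
|---|---|
| 46/50 | 80.8% |
| 47/50 | 83.5% |
| 48/50 | 86.3% |
| 49/50 | 89.4% |
| 50/50 | 92.9% |

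A result of 46/50 would be declared superior, yet it does not exclude a PEG+RBV rate of 82% or 85% (exact p against 85% = 0.23). An upward rejection of 85% needs 48/50, and of 90% needs 50/50.

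**The case against.** **The SAP does not claim superiority to PEG+RBV.** A reader might infer that it does. SAP 6.1.2 words superiority as relative to 80%, its efficacy section does not name PEG+RBV, and Protocol 9.6.2 speaks only of a comparison. This stands. The problem is the unqualified step from the protocol's PEG+RBV label to the SAP's word superiority.

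**The interval is already planned.** This stands too, but nothing in the plan ties the conclusion to it.

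**Larger error rates are tempting.** At 88% and 90% the n = 50 figures would be 26.8% and 43.1%, and the pooled test of 100 would give 16% to 25% at 85%. The documents supply no rate as high as 88%, and SAP 6.4 replaced the pooled test. These figures do not measure the final plan.

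**80% cannot be shown to be too low for this trial.** The 80% and the background statement rest on different sources, and an inequality is not a range. Up to 20 subjects may be treatment-experienced (Protocol 3.1.2), and no PEG+RBV rate is given for that mix. So the documents show an unreconciled inconsistency, not a wrong benchmark.

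**The SVR24 argument is weak.** A reader might infer that the historical GT-2/3 figure is an SVR24 rate, and so understates SVR12. Protocol 1.1 attaches that label to the GT-1 clause, so carrying it over is inference. SAP 3.5.1 treats the two endpoints as highly correlated.

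**The adolescent test is already done.** SAP 6.1.3 reports it in the past tense under a separate SAP, which is not available here and may contain qualifications. Nothing new can be pre-stated for that group.

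**Efficacy is secondary.** The Treatment Phase primary endpoint is safety, and any single-arm test against a constant has this property. That limits the importance, but does not remove the need to say what rejection means.

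**Conclusion.** The concern holds as a limit on interpretation. The exact test is valid for its stated null and the power arithmetic reproduces. A p-value below 0.05 against 80% nevertheless does not by itself support an advantage over PEG+RBV, because the protocol elsewhere reports that regimen above 80% in the same genotypes.

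The size depends on how far above. With exactly 50 subjects, the chance of declaring superiority in a single age-group test for a regimen only equal to PEG+RBV stays close to nominal if the true rate is 81% (2.7%), is modestly raised at 82% (4.0%), and reaches 11.2% at 85%. Those three rates are assumptions; the documents do not say which is nearest. What the data can support without any assumed rate is the lower confidence limit, and the plan should say so.

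**What to change.** - In SAP 6.1.2 and 6.1.3, and in the report, keep the exact test and the adolescents-first order. State that p below 0.05 shows only that SVR12 exceeds a fixed 80% benchmark.
- Limit any claim of advantage over PEG+RBV to historical rates below the lower 95% Clopper-Pearson limit already planned.
- Add exact tests at higher benchmarks, for example 85% and 90%, as sensitivity analyses. Pre-state them for the 3 to under 12 group before its test is run, and label them post hoc for adolescents.
- In Protocol 1.1 and 9.6.2, reconcile 80% with the above-80% statement and make clear whether each is an SVR12 or SVR24 rate. Give the derivation of 80% from its source.

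The cost is wording and two further exact p-values per age group, from data already being collected. No subjects or visits are added. The downside is a less favourable headline claim when the result is only just above 80%.
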